## **1.4 Masking**

This study is double-masked, with subjects randomized to use Test 1, Test 2, and Control in the assigned eyes and lens sequence. The Investigators, Investigators' staff (other than unmasked study coordinators), subjects, and Sponsor personnel (other than the Lead Clinical Site Manager, site monitors and unmasked data managers) involved in reporting, obtaining, and/or reviewing the clinical evaluations will not be aware of the specific treatment (lens and lens sequence) being administered. This level of masking will be maintained throughout the conduct of the study. Subjects will be assigned lens sequence in numerical order; the randomization schedule will be blocked to ensure a balance of study lens sequence allocations within investigational sites. The randomization scheme will be generated and maintained by the Sponsor. Individual subjects may be unmasked only once all study data have been verified and validated and the database has been locked. In the event of a medical emergency where the knowledge of subject treatment is required, an individual Investigator will have the ability to unmask the lens sequence assignment for a specific subject.

## **1.5 Interim Analysis**

No interim analyses are planned for this study.

## **2 Analysis Sets**

### **2.1 Safety Analysis Set**

The Safety Analysis Set will include all subjects/eyes exposed to any study lens. Safety analysis will be conducted using the safety analysis set on a treatment-emergent basis. For treatment-emergent safety analysis, subjects/eyes will be categorized under the actual lens exposed.

## 2.2 Full Analysis Set

The Full Analysis Set (FAS) will include all randomized subjects who satisfy the following criteria:

- Exposed to any study lens
- No biomicroscopy findings at screening as described in exclusion criterion # 5 or no corneal staining at Visit 3 as described in exclusion criterion # 5. If return visit is required for reassessment of corneal staining, only final value will be recorded in EDC and considered for this criterion.
- No current or history of pathological dry eye in either eye (exclusion criterion #6)
- No current or history of herpetic keratitis in either eye (exclusion criterion #7)
- No eye injury in either eye within twelve weeks immediately prior to enrollment for this trial (exclusion criterion #8)
- No history of intolerance or hypersensitivity to any component of the study lenses or solutions (exclusion criterion #9)

These critical deviation criteria will be identified in the Deviations and Evaluability Plan. Each subject will be classified according to the respective lens in the randomized lens, irrespective of the exposure. FAS will serve as the primary analysis dataset for all efficacy evaluations.

## 3 Subject Characteristics and Study Conduct Summaries

Subject characteristics and study conduct summaries include tables and listings such as a subject disposition, demographics (age, gender, race, ethnicity) and subject accounting by lens and/or lens sequence, listings of lens sequence assignment by investigator, discontinuation and subjects excluded from key analysis set with reason. All descriptive summary statistics will be displayed with n and % for categorical data, and with mean, standard deviation, median, minimum, and maximum for continuous data.

Demographic information will be summarized based on the safety and full analysis sets by lens sequence group.

## 4 Efficacy Analysis Strategy

This study defines one primary endpoint [REDACTED] The FAS will serve as the primary set for [REDACTED] efficacy analyses.

[figure not shown]
Descriptive summaries will be provided by Test 1, Test 2, and Control. Data for the control lens will be separated into those collected with Test 1 worn on the contralateral eye and those collected with Test 2 worn on the contralateral eye.

All data obtained in evaluable subjects/eyes will be included in the analysis. No imputation for missing values will be carried out for the efficacy analysis.

### 4.1 Efficacy Endpoints

#### Primary Endpoint

- Average of corneal staining areas observed (expressed as a percent) taken over the 5 regions: central, superior, nasal, inferior, and temporal, after 2 hours of lens wear.

## 4.2 Efficacy Hypotheses

[figure not shown]
No inferences are to be made on the primary [REDACTED] endpoint [REDACTED] therefore, no hypotheses are formulated.

[figure not shown]
## 4.3 Statistical Methods for Efficacy Analyses

### 4.3.1 Primary Efficacy Analyses

The average of corneal staining areas observed (%) taken over the 5 regions: central, superior, nasal, inferior, and temporal will be calculated for each test lens and the corresponding control. Corneal staining for each of the region will also be summarized.

Only descriptive summary statistics with mean, standard deviation, median, minimum, and maximum will be provided.

#### **4.4 Multiplicity Strategy**

No multiplicity adjustment needs to be considered for the efficacy variables as no inferences will be made.

#### **4.5 Subgroup Analyses and Effect of Baseline Factors**

Not applicable.

#### **4.6 Interim Analysis for Efficacy**

Not applicable.

### **5 Safety Analysis Strategy**

#### **5.1 Safety Endpoints**

The safety endpoints are:

- Adverse events
- Biomicroscopy findings
  - Limbal hyperemia
  - Bulbar hyperemia
  - Conjunctival staining
  - Corneal vascularization
  - Corneal epithelial edema
  - Corneal stromal edema
  - Conjunctival compression/indention
  - Chemosis
  - Palpebral conjunctival observations

- Corneal infiltrates
- Other findings
- Device deficiencies

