**Exclusion Criteria:**

1. Any anterior segment infection, inflammation, abnormality or disease (including systemic) that contraindicates contact lens wear, as determined by the Investigator.
2. Any use of systemic or ocular medications for which contact lens wear could be contraindicated, as determined by the Investigator.
3. History of refractive surgery or plan to have refractive surgery during the study or irregular cornea in either eye.
4. Ocular or intra-ocular surgery (excluding placement of punctal plugs) within the previous 12 months or planned during the study.
5. Biomicroscopy findings at screening that are moderate (grade 3) or higher and/or:
  - Corneal vascularization that is mild (grade 2) or higher.
  - Corneal staining:
    - Type 2 (macropunctate) or greater corneal staining in any region in either eye.
    - Sum of the types of corneal staining greater than or equal to 4 across all 5 corneal regions (central, nasal, temporal, superior, inferior) in either eye.
    - Corneal staining covering  $\geq$  20% in any

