**Sponsor:**

Alcon Research, Ltd.  
[name]  
[name]

**Protocol Number:** CLY935-E002

upon the FAS.

The primary endpoint is the average corneal staining area, where the average is taken over five regions and expressed in percentage. Data will be presented by each test coating with the corresponding control lens worn contralaterally. Summary statistics will be provided. No hypotheses are formulated; therefore, no inferences will be made.

All data from evaluable subjects will be included in the efficacy analysis, and no imputation for missing values will be performed.

Each safety variable will be summarized descriptively. Adverse events will be classified as treatment-emergent or pre-treatment. Counts and percentages will be provided by relationship to device, and separate tables will be generated for ocular and nonocular AEs. Counts and percentages in each grade category will be presented for each biomicroscopy parameter. Device deficiencies will also be tabulated. Supporting subject listings will be provided as applicable. No inferential testing will be performed for safety analysis.

Sample Size Justification

The proposed sample size of 32 is adapted from Andrasko (2008) and allows for a balanced allocation of lens sequences.

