## 2 OVERVIEW OF STUDY PLAN

Procedure/ Assessment	Visit 1 Screening / Baseline / Pair 1 Dispense	Visit 2 Pair 1 Follow- up 2 hrs (-15 min/+1 hr)	Visit 3 Baseline / Pair 2 Dispense (+2 to 8 days)	Visit 4 Pair 2 Follow- up / Exit 2 hrs (-15 min/+1 hr)	Unsched.
Informed Consent	✓	-	-	-	-
Demographics	✓	-	-	-	-
Medical History	✓	✓	✓	✓	✓
Concomitant Medications	✓	✓	✓	✓	✓
Inclusion/Exclusion	✓	-	-	-	-
Randomize subject	✓	-	-	-	-
Reassess corneal health	(✓)	-	✓	-	-
VA w/ spectacles  (OD, OS, OU as needed, Snellen distance)	✓	✓	✓	✓	(✓)
Manifest refraction 	✓	(✓)	(✓)	(✓)	(✓)
BCVA  (OD, OS, Snellen distance with manifest refraction)	✓	(✓)	(✓)	(✓)	(✓)
Biomicroscopy [including Corneal Staining, per region (type, area)] 	✓	✓	✓	✓	✓
Dispense study lenses	✓	-	✓	-	-
AEs	✓	✓	✓	✓	✓

Procedure/ Assessment	Visit 1 Screening / Baseline / Pair 1 Dispense	Visit 2 Pair 1 Follow- up 2 hrs (-15 min/+1 hr)	Visit 3 Baseline / Pair 2 Dispense (+2 to 8 days)	Visit 4 Pair 2 Follow- up / Exit 2 hrs (-15 min/+1 hr)	Unsched.
Device deficiencies	✓	✓	✓	✓	✓
Exit Form	(✓)	(✓)	(✓)	✓	(✓)

 Source only Primary endpoint

█

(✓) assessment performed as needed

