### 10.2.3 Visit 3 (+ 2 to 8 Days) –Baseline/Pair 2 Dispense

1	Obtain information on any changes in medical health and/or the use of concomitant medications.
2	Record any adverse events or device deficiencies that are observed or reported, including those associated with changes in concomitant medication dosing.
3	Review subject compliance with washout period. If lenses have been worn, reschedule Visit 3 to allow for the washout period.

4	
Perform Snellen VA with habitual spectacles.
 

• OD, OS, distance only

 
Note: If this VA with spectacle correction shows a decrease of 2 lines or more versus Visit 1 baseline VA with spectacle correction, then BCVA with MR is required to confirm a potential loss in VA for AE reporting requirements (see Section 12).

5	
Perform slit-lamp biomicroscopy (without contact lenses) to evaluate the following:
 

• Limbal hyperemia

• Bulbar hyperemia

• Corneal staining – 5 regions (type, area)

• Conjunctival staining

• Corneal vascularization

• Corneal epithelial edema

• Corneal stromal edema

• Conjunctival compression/indentation

• Chemosis

• Palpebral conjunctival observations

• Corneal infiltrates

• Other findings

6	
Review exclusion criteria (#5) related to corneal staining.
 

• If subject fulfills criteria, go to step 7.

• If subject shows unacceptable corneal staining, they will be permitted to return within 7 days to be reassessed. The Investigator will determine if it is permissible for the subject to use preservative-free lubricating drops prior to returning for reassessment. The use of preservative-free eye drops should not be considered a treatment, but rather a palliative measure to reduce corneal staining, and as such should not trigger an adverse event. If upon reassessment corneal staining remains unacceptable, discontinue the subject from the trial.

7	
Based on the randomized lens sequence assignment, have the subject insert the Pair 2 study lenses to be evaluated, being careful to maintain the correct OD and OS lens assignments.
 
Note: Keep all lidding foils of lenses used during lens fit process for study lens accountability.

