## **11.7 Safety Analysis**

The safety endpoints for this study are AEs, biomicroscopy findings, and device deficiencies.

Descriptive summaries (counts and percentages) for ocular and nonocular AEs will be presented by MedDRA Preferred Terms. In addition to an overall presentation of AEs, reports will be generated for significant non-serious AEs, and serious AEs. AEs leading to study discontinuation will be identified. Individual subject listings will be provided, as necessary.

Pre-treatment and between-treatment-period AEs will be presented, with subject listings, separated from treatment-emergent AEs. A pre-treatment AE is an event that occurs after signing informed consent but prior to exposure to a study lens. A between-treatment-period AE is an event that occurs after last exposure to Period 1 study lens but prior to exposure to Period 2 study lens.

Each biomicroscopy parameter will be tabulated by its grade. For each biomicroscopy parameter, counts and percentages of eyes that experience an increase of  $\geq 2$  grades from baseline (Visit 1 for Period 1 and Visit 3 for Period 2) to any subsequent visit will be presented. A supportive listing will be generated which will include all biomicroscopy data from the affected period for these eyes experiencing the increase, with the following variables: lens, Investigator, subject, age, sex, visit, eye, parameter, baseline value, and value at the visit.

Two listings (prior to exposure of study lenses, treatment-emergent) of device deficiencies, as recorded on the Device Deficiency Form, will be provided. Additionally, each device deficiency category will be tabulated.

No inferential testing will be done for safety analysis.

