## **5.2 Safety Hypotheses**

There are no formal safety hypotheses in this study. The focus of the safety analysis will be a comprehensive descriptive assessment of safety endpoints listed in Section 5.1.

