### **5.3.2 Biomicroscopy Findings**

For each biomicroscopy finding, all exposed eyes will be summarized; hence, the unit will be eye. A summary of grade category counts and percentages will be presented for each parameter by visit.

Each biomicroscopy parameter will be tabulated by its grade. For each biomicroscopy parameter, counts and percentages of eyes that experience an increase of  $\geq 2$  grades between baseline (Visit 1 for Period 1 and Visit 3 for Period 2) and any subsequent visits will be presented. A supportive listing will be generated and will include all biomicroscopy data from the affected period for these eyes experiencing the increase, with the following variables: lens, Investigator, subject, age, sex, visit, eye, parameter, baseline value, and value at the visit.

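### SAP 5.1 leaves corneal staining out of the safety endpoints, so no visible safety-set output counts eyes by staining type and lens actually worn

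*SAP*

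**What the plan says.** **Protocol.** The slit-lamp step at each of the four visits (10.2.1 to 10.2.4) lists 12 items, one of which is corneal staining by type and area in five regions. The schedule in Section 2 has a single row for it: "Biomicroscopy [including Corneal Staining, per region (type, area". For the safety analysis, the synopsis states: "Counts and percentages in each grade category will be presented for each biomicroscopy parameter". Section 11.7 repeats this, "Each biomicroscopy parameter will be tabulated by its grade", and adds a count of eyes rising 2 or more grades from the same period's baseline. Neither place makes an exception for staining.

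**SAP.** Section 5.1 begins "The safety endpoints are" and lists 11 biomicroscopy items, without corneal staining and without a reason. Section 5.2 then says: "The focus of the safety analysis will be a comprehensive descriptive assessment of safety endpoints listed in Section 5.1". Section 5.3.2 sets the unit: "For each biomicroscopy finding, all exposed eyes will be summarized; hence, the unit will be eye". Under SAP 2.1 the safety set is classified by the lens actually worn; under SAP 2.2 the FAS is classified by the randomized lens.

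**Where staining does appear.** SAP 4.1 and 4.3.1 make mean percent area over the five regions the primary endpoint, with a further summary by region. The only statistics offered are mean, SD, median, minimum and maximum. A footnote in Protocol 12.1 says staining that the investigator judges predominantly solution-related is not recorded as an AE.

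**The concern.** Protocol 5.2 says the coatings have had no clinical evaluation, and it names a toxicity response first among the potential harms. The type scale in the synopsis separates fine punctate staining (Type 1) from coalesced (Type 3) and patch (Type 4) staining, and that distinction is relevant to safety. Type is recorded per region at every visit, yet a reader of the visible safety tables could not say how many eyes reached Type 3 or 4 on each lens actually worn. Mean area does not supply that count. The AE tables may not supply it either, because every lens is pre-cycled in the solution and the 12.1 footnote could therefore apply widely.

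**Working it through.** **1. List comparison.** Protocol 10.2.1 to 10.2.4: 12 items at each visit. SAP 5.1: 11 items in the same order. The difference is 12 − 11 = 1, corneal staining, and the SAP adds no item of its own. The entry for other findings cannot absorb it, because the protocol lists that entry alongside corneal staining.

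**2. Could another visible output supply the count?**

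| Output | Set and lens | Why it does not give eyes by staining type and actual lens |
|---|---|---|
| Primary summary (SAP 4.1, 4.3.1) | FAS, randomized | Area only |
| Regional summary (SAP 4.3.1) | FAS, randomized | Not expressly limited to area, but type is not named |
| Redacted efficacy endpoints | FAS, randomized, from the visible text | May cover type, but not on the safety set |
| Grade tables (SAP 5.3.2) | Safety set, actual | Read with 5.1 and 5.2, cover the 11 listed items |
| Listing (SAP 5.3.2) | Safety set, actual | Shows all biomicroscopy data for an eye, but only if a parameter covered by the rule rises 2 or more grades |
| AE tables | Safety set, actual | Predominantly solution-related staining is kept out by Protocol 12.1 |

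**3. Area does not convey type.** Assumed values for illustration: patch staining over 10% of one region and none elsewhere gives (10 + 0 + 0 + 0 + 0)/5 = 2%. Micropunctate staining over 2% of every region gives (2 + 2 + 2 + 2 + 2)/5 = 2%. The primary endpoint is the same for both eyes; the maximum types are 4 and 1.

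**4. Size of the missing table.** The plan's sample size of 32 is not derived from a power formula. Its stated balance does check: 32/4 sequences = 8 per sequence. Post-wear examinations with 32 completers: 32 subjects × 2 eyes × 2 periods = 128, made up of 32 (Test 1) + 32 (Test 2) + 64 (Control). If all of about 35 enrolled wore both pairs, the split would be 35, 35 and 70.

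**5. Would the existing 2-step rule work on type?** Exclusion criterion 5 bars "Type 2 (macropunctate) or greater corneal staining in any region in either eye", and Visit 3 repeats the check: "Review exclusion criteria (#5) related to corneal staining". An eligible eye therefore starts each period at maximum Type 0 or 1.
- From baseline 0, a rise of 2 or more is reached by post-wear Types 2, 3 and 4.
- From baseline 1, it is reached by Types 3 and 4 (3 − 1 = 2).
- From baseline 2 (an ineligible eye dispensed in deviation), Type 3 is a rise of 3 − 2 = 1 and is missed.

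The rule catches all Type 3 and 4 eyes only when baseline is 0 or 1. The safety set keeps every exposed eye, including ineligible ones, so a separate listing is needed.

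**6. What a count could convey.** One eye in 32 is 1/32 = 3.1%, with an exact (Clopper-Pearson) two-sided 95% interval of 0.1% to 16.2%. For 0 in 32 the upper limit is 1 − 0.025^(1/32) = 10.9%. These are for scale only, since the plan makes no inference. The documents give no expected frequency of Type 3 or 4 staining, so the number of eyes affected cannot be estimated.

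**The case against.** The strongest reply is that the protocol itself separates the two. Its synopsis puts corneal staining under primary efficacy assessments and biomicroscopy under safety, and the endpoints follow the same split. The tabulation rule speaks of grade, whereas staining is recorded as type and percent area, and the 12.1 footnote says the scale differs. On this reading SAP 5.1 follows the protocol's layout. This stands as a plausible reason, and it means a table of staining type needs a new derived variable. It does not settle the matter: exclusion criterion 5, Section 2 and Section 10.2 all place staining within biomicroscopy, and the SAP states no reason.

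A second reply is that 5.3.2 speaks of every biomicroscopy finding, and that 5.2 gives the focus of the safety analysis, which is not clearly an exclusion. If so, staining would be tabulated anyway. The wording does leave this open, but a programmer working from the 5.1 list would not produce the table.

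Third, parts of the efficacy sections are redacted and may hold a type endpoint. Protocol Section 11 gives counts and percentages for categorical variables, so such an endpoint could be tabulated. That also stands, but the visible text puts efficacy evaluations on the FAS by randomized lens.

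Fourth, the two sets differ only for exposed subjects dropped from the FAS and for eyes given a lens other than the one randomized, and no figure suggests many of either. Coalescent or patch staining that is not solution-related is already reportable as a significant non-serious AE. Both are correct and keep the point small.

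**Conclusion.** The point holds as a minor gap. SAP 5.1 carries 11 of 12 biomicroscopy items, and no visible output on the safety analysis set counts eyes by staining type and lens actually worn. The success rule, the primary analysis and the sample size are untouched. The conclusion rests on reading 5.2 as tying the safety analysis to the 5.1 list, and on the unredacted text only.

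Three stronger readings are tempting and are not supported:
- A reader might infer that the SAP plainly contradicts the protocol. The synopsis split and the separate scale make a deliberate choice possible.
- A reader might infer that staining type is analysed nowhere. Redacted endpoints and the regional summary may cover it on the FAS.
- A reader might infer that severe solution-related staining can never be an AE. Protocol 12.1 excludes predominantly solution-related staining, but 10.4 requires signs of suspected sensitivity or intolerance to a study treatment to go on an AE form, and 12.2 requires clinically relevant changes to be reported whatever the cause. AE capture is unresolved, not closed.

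**What to change.** - Add corneal staining type to SAP 5.1, as a derived variable: the maximum type over the five regions per eye.
- Under SAP 5.3.2, tabulate it by visit and actual lens on the safety analysis set, and count eyes rising 2 or more types from the same period's baseline.
- List every eye with post-wear Type 3 or 4, whatever its baseline and attributed cause.
- If the omission is intended, say so and why in SAP 5.1.
- Separately, reconcile Protocol 10.4, 12.1 and 12.2 on AE reporting of clinically relevant solution-related staining.

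The cost is one derived variable, one table and one listing, from data already collected at every visit. The downside is that staining then appears in both efficacy and safety outputs, and some of it is expected, so the safety table needs a note to that effect.

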## **5.2 Safety Hypotheses**

There are no formal safety hypotheses in this study. The focus of the safety analysis will be a comprehensive descriptive assessment of safety endpoints listed in Section 5.1.

## **5.3 Statistical Methods for Safety Analyses**

The analysis set for all safety analyses is the safety analysis set as defined in Section 2.1. The safety variables will be summarized descriptively. Baseline will be defined as the last measurement prior to exposure to the study lens on Visit 1 for Period 1 and Visit 3 for Period 2.

### **5.3.1 Adverse Events**

The applicable definition of an Adverse Event (AE) is in the study protocol. All AEs occurring from when a subject signs informed consent to when a subject exits the study will be accounted for in the reporting.

Pre-treatment and between-treatment-period AEs will be presented, with subject listings, separated from treatment-emergent AEs. A pre-treatment AE is an event that occurs after signing informed consent but prior to exposure to a study lens. A between-treatment-period AE is an event that occurs after last exposure to Period 1 study lens but prior to exposure to Period 2 study lens.

Descriptive summaries (counts and percentages) for ocular and non-ocular AEs will be presented by Medical Dictionary for Regulatory Activities (MedDRA) Preferred Terms. In addition to an overall presentation of AEs, reports will be generated for significant non-serious AEs, and serious AEs. AEs leading to study discontinuation will be identified. Presentation of ocular AEs will be by eye. Individual subject listings will be provided, as necessary.

Individual subject's listings will be provided for both pre-treatment and between-treatment-period AEs.

